7.0 STATISTICAL CONSIDERATIONS

7.1 Overview of Statistical Considerations

The overall statistical approach follows from the goal of measuring the population effect of the MC ASI. This is achieved by estimating HIV incidence using two nationally representative, household-based samples of the Swaziland population, one before and one after the MC ASI (Cohorts A1 and A2). The study is powered for primary objective # 1a, with at least 80% power to detect a 45% reduction in the HIV seroincidence rate of HIV-uninfected men 18-49 in Swaziland from pre to post-MC ASI.

A longer longitudinal cohort (Cohort B) of the highest risk age group of HIV uninfected men and women from Cohort A2 will measure HIV incidence at an additional time point, at a greater period post- MC ASI campaign.

The two-stage cluster sampling scheme is designed to achieve a nationally representative sample of households. All consenting, eligible HIV uninfected men and women 18-49 will be followed to estimate HIV incidence. Weighted estimation will be used in order to achieve population based estimates of HIV seroincidence, using weights corresponding to the national household sample achieved.

The number of HIV uninfected men is chosen to achieve a nationally representative sample of men to have at least 80% power to detect 45% reduction in the HIV seroincidence rate of HIV uninfected men 18-49 in Swaziland from pre to post-MC ASI. The number of households approached will yield a sample of women from which we can estimate the reduction in HIV seroincidence rate of HIV uninfected women 18-49 in Swaziland from pre to post-MC ASI.

The longer-term longitudinal cohort, Cohort B, will be the subset of men aged 25-34 and women aged 18-25 from Cohort A2. Cohort B will be used to estimate the trend in

seroincidence following the MCASI campaign. Cohort B will also be used to assess the trend in sexual risk behaviors following the MC ASI campaign.

The pre vs. post MC ASI comparison of seroincidence rates does not allow causal interpretation of the MC ASI as the sole mechanism influencing observed change in HIV seroincidence rates. Likewise the assessment of trends in sexual behaviors over time does not allow causal interpretation of the MC ASI as the sole mechanism influencing observed change in levels of sexual risk behaviors. In this non-randomized design, other changes occurring over the same time period could also influence HIV seroincidence rates and sexual risk behaviors. The use of a nationally representative sample in each seroincidence cohort does allow a valid assessment of the population based change in HIV seroincidence in men and women 18-49 before and after the period in which the MC ASI occurred and sexual risk behaviors among the younger men (25-34) and women (18-24) at higher risk of HIV infection during and after the MC ASI.

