For surgical candidates identified as HIV-infected during PITC, the following services will be provided, as is customary for all persons newly diagnosed with HIV in Swaziland:

- the recommendation and availability of VCT for sex partners;
- counseling regarding the lack of HIV prevention benefit from MC; and,
- referrals for HIV prevention, care, and treatment services

Efforts are underway to align MC service delivery locations with existing clinical staging and HAART-initiation centers to facilitate linkages between the MC program and HIV care and treatment program.

Approximately 35FTE service delivery teams during peak times will be required to meet the program target of reaching up to 175,000 boys and men with a comprehensive package of MC services in the 12-month period from January to December 2011. To minimize strain on existing health systems, the GKOS plans to utilize international human resources and mobile MC services to accomplish the campaign's strategic goals. It is planned that entire surgical teams—physician surgeons, nurses, surgical assistants,

cleaners, counselors—will be transported along with all necessary equipment and supplies to designated locations throughout the country. They will provide services in temporarily erected minor surgical theaters or in existing health facilities, schools or other buildings outfitted for short-term provision of MC services.

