2.6 Hypotheses

- 1) HIV incidence among men ages 18-49 in Swaziland will decrease over time, coinciding with national HIV prevention, care and treatment programs, including the MC ASI.
- 2) HIV incidence among women ages 18-49 in Swaziland will decrease over time, coinciding with national HIV prevention, care and treatment programs, including the MC ASI.
- 3) HIV incidence among men and women in the highest risk age groups in Swaziland, men ages 25-34 and women ages 18-24, observed longitudinally, will decrease over time, coinciding with national HIV prevention, care and treatment programs, including the MC ASI.
- 4) HIV incidence among men in Swaziland will differ by male circumcision status, measured after completion of the MC ASI.
- 5) The proportion of individuals with CD4 counts in each of the following categories will be approximately 25%: 0-200, 201-350, 351-500, 501 cells/mm³ and above.
- 6) The proportion of HIV-infected men and women ages 18-49 who have a CD4 count <350 cells/mm³ and who report no current ART use is 20-40%.

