3.0 OBJECTIVES

3.1 Primary Objectives

- 1a) To estimate HIV incidence rates in a household-based, nationally representative sample of men ages 18-49 before and after completion of the MC ASI.
- 1b) To estimate HIV incidence rates in a household-based, nationally representative sample of women ages 18-49 before and after completion of the MC ASI.

- 2a) To estimate HIV incidence rates in a highest risk age subset of the household-based, nationally representative sample, namely men ages 25-34, for an additional 6-18 months after the MC ASI completion.
- 2b) To estimate HIV incidence rates in a highest risk age subset of the household-based, nationally representative sample, namely women ages 18-24, for an additional 6-18 months after the MC ASI completion.
- 3) To estimate HIV incidence rates of circumcised men as compared to uncircumcised men in a household-based, nationally representative sample of men after completion of the MC ASI.

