4.0 STUDY DESIGN

The study will utilize a combination of methods to achieve the objectives listed above in section 3.0. For all primary objectives and secondary objectives 1 through 7, three cohorts will be recruited and followed as part of this evaluation. Two short term cohorts of household-based representative samples of HIV-uninfected individuals will be recruited and followed: the first (Cohort A1), enrolled approximately six months before the MC ASI will be followed for six months; the second (Cohort A2), enrolled 12 months after the conclusion of MC ASI will be followed for 12 months. Cohorts A1 and A2 are selected independently. The third longitudinal cohort (“Cohort B”) will follow a subset of Cohort A2 participants who are HIV-uninfected individuals in the highest-risk age groups for HIV acquisition (18-24 years of age for women and 25-34 years of age for men), for an additional 6-18 months (beyond the 12 months of Cohort A2).

- *Primary Objectives 1a & 1b: To estimate HIV incidence rates in a household-based, nationally representative sample of men and women ages 18-49 years before and after completion of the MC ASI*
- *Primary Objective 2a & 2b: To estimate HIV incidence rates in the highest risk age subsets of the household-based, nationally representative sample, namely men ages 25-34 years and women ages 18-24 years, for an additional 6-18 months after the MC ASI completion.*

HIV incidence will be determined by following separate sequential household-based representative samples of HIV-uninfected men and women for six and 12 months, before and after MC ASI, respectively, to directly measure new HIV infections. These two sequential longitudinal cohorts (independently selected), separated in time by approximately 24 months, will be used to measure baseline (before the MC ASI) and post-MC ASI program incidence rates. See Figure 3. (Note: In the Figures 3-5, month 0 is January 2011, the time of the launch of MC ASI. Thus pre-MC ASI baseline begins before Month 0.)

Men and women from Cohort A2 in the highest-risk age groups for HIV acquisition who are HIV-uninfected at Month 36 are eligible to remain in a longer-term longitudinal

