cohort (Cohort B). These individuals will be retested for HIV at approximately Month 42. See Figure 4. Thus changes in HIV incidence among men and women in the high-risk age groups can be compared with changes in HIV incidence from the sequential longitudinal cohorts, and the overall impact of MC ASI on new HIV infections will be observed. See Figure 5.

Additionally, for secondary objective 8 and 9, a cross-sectional observational survey of a household-based, nationally representative sample of HIV-seropositive individuals will be identified from Pre-Cohort A1 participants. This subset of individuals will be recruited for participation in Cross-Sectional C. Recruitment will occur approximately six to twelve months after participation in Pre-Cohort A1.

Below is the time frame for each of the three cohorts and the additional cross-sectional measurement. Each is presented in a figure, and the study objectives for each cohort are described.

Cohort A1: Baseline (pre MC ASI) short-term cohort of household-based nationally representative sample of men and women 18 – 49 years of age

- Enrollment (Month -6)
- Follow-up (Month 0)

Cohort A2: Post MC ASI short-term cohort of household-based nationally representative sample of men and women 18 – 49 years of age

- Enrollment (Month 24)
- Follow-up (Month 36)

Cohort B: Longer-term prospective cohort of household-based nationally representative sample of men and women in the highest risk age groups (men 25-34 years, women 18-24 years)

- Enrollment (Month 36)
- Follow-up (Month 42)

Cohort C: Cross-sectional, observational survey of a household-based, nationally representative sample of HIV-infected men and women 18-49 years of age

- Enrollment (Month 0)

[figure not shown]
Primary Objectives 1a & 1b and Secondary Objective 1

Data collected during enrollment and follow up of Cohort A1 and Cohort A2 will be used to estimate HIV incidence rates in a household-based representative sample of men and women 18-49 years old before and after completion of the MC ASI and to examine the association of baseline demographic characteristics with HIV incidence.

Secondary Objectives 1, 2, 3, 4a, 5, 6

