4.2 How study design meets objectives and addresses research questions

The study design incorporates two different strategies for measuring the change in seroincidence. To measure the population effect of the MC ASI campaign on HIV infection in Swaziland, we plan two independent household based samples, one prior to the campaign, one 12 months after the completion of the campaign. Each gives an

independent population “snapshot” of the current rates of infection. The second strategy enrolls a cohort of men and women in the ages at highest risk prior to the MC ASI and measures that seroincidence in this group for an additional 6-18 months after the campaign’s completion. There are several reasons for this hybrid approach. Two sequential short term cohorts provide two similar ‘snapshots’ of HIV incidence before and after the ASI campaign and coinciding with scale-up of other prevention programs. These two cohorts are representative of the national population and the HIV seroincidence estimates before and after ASI are therefore likely to represent actual changes in the epidemic. The use of a more traditional longitudinal cohort is conceptually familiar from randomized placebo controlled clinical trials; here it is used to follow HIV incidence among young adults in the highest incidence age groups over an additional 6-18 month period.

The comparison of HIV incidence rates between circumcised and uncircumcised men offers insight into the role played by MC in reducing HIV infection in the cohort and in the general population, if observed.

Blood specimens from persons identified as HIV-infected *during pre-cohort surveys* (A1 and A2) will be collected to measure viral load. These data will be used to determine the proportion of HIV infected persons with undetectable viral load in the community. The proportion of undetectable viral load at the baseline pre-cohort survey will be compared to the post-MC ASI pre-cohort survey to explore the potential effect of scale up of the ART program and viral suppression on reduced HIV incidence in the general population, if observed.

Blood specimens to measure CD4 count will be collected using a multistage clustered random sample of persons who were identified as HIV-seropositive at the pre-cohort survey for Cohort A1 (T1). These data will be used to estimate the CD4 count distribution, viral load distribution, and self-reported ART use among HIV-infected individuals at the population-level.

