Surveys of sexual risk behavior and exposure to sexual risk reduction campaigns of men and women will be administered as part of the pre-cohort survey before and after the MC ASI. In addition, men and women in the longer term cohort (Cohort B) will provide sexual risk behavior information at all scheduled study visits. Repeated measures of sexual risk behaviors and exposures to sexual risk reduction campaigns over time, allows for examination of whether risk behavior changes may be coincident with MC ASI and reduced HIV incidence, if observed.

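### Cohort B is first enrolled two years after the campaign ends, so the protocol's claims that it starts before the campaign and shows behaviour during it are wrong, and Objectives 2a/2b have no single time window.

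*Protocol*

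**What the plan says.** **Calendar.** Section 4.0 sets the clock: "month 0 is January 2011, the time of the launch of MC ASI". Section 2.1 gives the campaign a "12-month period from January to December 2011". Section 4.0 enrols Cohort A2 at Month 24 and follows it to Month 36. Cohort B is drawn from A2 members still HIV-negative at Month 36 and retested at about Month 42. Section 6.6.5 and the incentives in section 9.3.3 also use Month 42.

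**Claims about Cohort B.** Section 4.2: "The second strategy enrolls a cohort of men and women in the ages at highest risk prior to the MC ASI". It adds that repeated behaviour measures "allows for examination of whether risk behavior changes may be coincident with MC ASI". Section 7.1 claims a valid assessment of "sexual risk behaviors among the younger men (25-34) and women (18-24) at higher risk of HIV infection during and after the MC ASI", although earlier in the same section Cohort B is said to give trends after the campaign. Hypothesis 3 (section 2.6) expects incidence in these age groups, "observed longitudinally, will decrease over time, coinciding with national HIV prevention, care and treatment programs, including the MC ASI".

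**Objectives 2a/2b.** Section 3.1 asks for incidence "for an additional 6-18 months after the MC ASI completion". The Schema and sections 4.0 and 5.1 count the 6-18 months from the end of A2's 12 months. Section 7.2 calls Cohort B a 6-month cohort. The power text in section 7.2 uses Months 24-42, and section 8.1.3 names only A1 and A2 when it describes the comparison.

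**The concern.** A cohort that starts two years after an intervention ends cannot describe what happened before or during it. Sections 4.2 and 7.1 credit Cohort B with that ability, for the age groups at highest risk.

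Two things are at stake. First, the only risk-behaviour analysis specific to men 25-34 and women 18-24 (section 8.1.4, item 4) compares Cohort B baseline with follow-up, and both points fall long after the campaign. A flat trend could be reported as no risk compensation, and a fall as a campaign effect. By then the same people are older and have been tested and counselled repeatedly, which section 4.4 itself names as a threat to validity.

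Second, Objectives 2a/2b are primary, yet different sections imply different windows and different person-time. The choice changes the power materially.

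**Working it through.** **Step 1: timing.** The campaign ends at about Month 12.

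- Cohort B: 36 - 12 = 24 and 42 - 12 = 30, so it covers 24-30 months after completion.
- First contact with any Cohort B member (A2 entry): 24 - 12 = 12 months after completion.
- An 18-month Cohort B follow-up would end at Month 36 + 18 = 54.

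No Cohort B member is observed in Months 0-12 or earlier, even after linking back to A2 data.

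**Step 2: the Objective 2 window.**

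| Source | Window implied |
|---|---|
| 3.1, counted from campaign completion | Months 18-30 (12 + 6 to 12 + 18) |
| Schema, 4.0, 5.1: beyond A2's 12 months | Month 36 to Months 42-54 |
| 4.0, 6.6.5, 7.2: one follow-up at 6 months | Months 36-42 |
| 7.2, men: 24-42 months after A1 ends (Month 0) | Months 24-42 |
| 7.2, women: 24-42 months following the MC ASI | Months 24-42 from launch, or 36-54 from completion |
| 8.1.3: only A1 and A2 named | Months 24-36 after the campaign |

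**Step 3: which window the stated power uses.** Inputs from section 7.2:

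- Men: 1,456 in A1 and 1,541 in A2/B; rate 5.0 per 100 person-years; rate ratio 0.50; loss 12% per year.
- Women: 2,183 in A2/B; rate 6.0; rate ratio 0.60; loss 10% per year. The A1 count is not given; I assume 0.29 x 7,106 = 2,061.
- Design effect 1.25; two-sided alpha 0.05.

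Formula (Wald test, Poisson regression): power = Φ(|ln RR| / √(1/E1 + 1/E2) - 1.96), where E = rate x person-years / 1.25. The same method returns Table 1's 6,289 person-years for 0.020 versus 0.011. It also returns the 68% and 82% stated for women under Objective 1b.

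Men, A1 versus Months 24-42, crediting completers only:

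- A1: 1,456 x 0.5 x 0.94 / 1.25 = 547 effective person-years, E1 = 27.4
- A2 plus B: 1,541 x 1.5 x 0.82 / 1.25 = 1,516, E2 = 1,516 x 0.025 = 37.9
- 0.693 / √(1/27.4 + 1/37.9) - 1.96 = 0.80, power 79%

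Ranges over four ways of crediting loss to follow-up:

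| Contrast | Men, 50% reduction | Women, 40% reduction |
|---|---|---|
| A1 v A2 plus B (Months 24-42) | 78.5-81.3% | 78.8-81.2% |
| A1 v A2 only (Months 24-36) | 71-75% | 72-75% |
| A1 v B only (Months 36-42, full stated B numbers) | 54-58% | 57-60% |
| A2 v B, both after the campaign | 63-67% | 66-70% |

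The stated figure of about 80% belongs to the first row. The second row is what section 8.1.3 literally describes. The third is what Objectives 2a/2b suggest if read as Cohort B alone.

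**Step 4: behaviour.** Section 8.1.4 item 4 has two parts: a comparison of the pre- and post-campaign surveys in all adults aged 18-49, and a baseline-to-follow-up comparison in Cohort B. Taking Cohort B baseline as its own enrolment, the second part compares Month 36 with Month 42. If the A2 survey were used as baseline, it would be Month 24, still 12 months after the campaign. Neither part states a pre/post contrast restricted to men 25-34 and women 18-24.

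**The case against.** Four points count against a harsher reading.

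- A reader might infer that Hypothesis 3 cannot be tested at all. The protocol does not support that. Section 7.2 sets the independent A1 age subset against Months 24-42, and section 8.1.3 lists 2a/2b under the pre/post comparison. Change since before the campaign can be estimated from independent samples. What is missing is follow-up of the same people across it.
- A reader might infer that Cohort B misses the window Objective 2 names. That holds only if 6-18 months is counted from campaign completion. On the definition in the Schema and sections 4.0 and 5.1, Cohort B does observe it. The defect is conflicting anchors.
- A reader might infer that risk behaviour in these ages is studied only in Cohort B. The pre/post surveys include these ages, and the section 4.2 sentence on coincidence with the campaign follows a description of those surveys as well as of Cohort B. Only the age-specific pre/post estimate is not spelled out.
- Late observation is defensible. Section 2.2 expects effects in women to lag by several years, Hypothesis 3 covers other national programmes too, and sections 2.3 and 7.1 disclaim sole attribution to the campaign. The promise of multiple follow-up observations in section 4.4 can also be met if the Month 36 and Month 42 tests are both counted.

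All four stand. None rescues the statements that Cohort B is enrolled before the campaign or that the younger groups' behaviour is assessed during it, and none settles which window Objective 2 means.

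**Conclusion.** The point holds as an error of statement and definition that should be corrected. Sections 4.2 and 7.1 attribute to the design properties it lacks, and they contradict section 4.0 and section 7.1's own description of post-campaign trends. Hypothesis 3's longitudinal wording fits no cohort that spans the campaign. Primary Objectives 2a/2b lack one anchor, one follow-up length and one named contrast.

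The stated power is not in error, but it is tied to A1 versus A2 plus B. Other readings cost from about 5 to 25 percentage points. The power ranges assume the planned numbers, the protocol's rates, loss and design effect, and an A1 count for women derived from the 29% share given for A2. The timing assumes the campaign ran as planned. A separate statistical analysis plan, not seen here, might name the contrast, but it would not make the two protocol statements true.

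**What to change.** 1. In sections 4.2 and 7.1, state that Cohort B is enrolled, and behaviour in these age groups is followed, after the MC ASI.
2. Use one anchor and one follow-up length for Objectives 2a/2b in the Schema and sections 3.1, 4.0, 5.1, 6.3, 6.6.5 and 7.2, and align the men's and women's wording in section 7.2.
3. In sections 2.6 and 8.1.3, state that Hypothesis 3 and Objectives 2a/2b are tested by the independent A1 age subset against A2 plus Cohort B (Months 24-42), accounting for attained age. Do not restrict this test to A1 versus A2, which lowers power from about 80% to about 71-75%.
4. In section 8.1.4 item 4, add an A1 versus A2 pre-cohort survey comparison of risk behaviour in men 25-34 and women 18-24. Report the Cohort B baseline-to-follow-up change only as a late post-campaign trend.

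The cost is protocol wording and one further analysis of data the study already plans to collect. The downside is a more modest claim for Cohort B.

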7.2 Sampling, including sample size and statistical power

A nationally-representative sample of men and women will be identified for both the baseline and post-intervention surveys and cohorts via a two-stage cluster-based sampling of 'enumeration areas' and households. Enumeration areas are sampling points defined by the 2007 Swaziland Population and Housing Census. A total of approximately 575 enumerations areas will be drawn from the census sample frame of all 2000 enumeration areas with a probability of selection proportional to the number of households within the enumeration area. The enumeration areas in urban versus rural areas will be proportional to the urban versus rural distribution of the population. Between November 2010 and May 2011, staff will conduct an exhaustive listing of households within each sampled enumeration area. During household listing, study staff will use Global Positioning Systems (GPS) receiver to record the geographic coordinates of each cluster and household. In the pre-MCASI cohort, approximately 14,884 households will be sampled, and 12,301 households will participate in the study. From these households we expect to identify, recruit, screen, and enroll a sample size of 5,823 men and approximately 7,106 women in the first seroincidence cohort (Cohort A1). In the post-MC ASI cohort, approximately 15,758 households will be sampled, and 13,024 households will participate in the study. From these households we expect to identify, recruit, screen, and enroll a sample size of 6,165 men and approximately 7,524 women in the second seroincidence cohort (Cohort A2). From Cohort A2, we expect approximately 25% of the men will be 25-34 years old, and 29% of the women will be 18-24 years old, yielding the longer, 6 month longitudinal cohorts of 1,541 men and 2,182 women (Cohort B).

Statistical power calculations for primary objectives are included as Appendix P.

Primary Objective #1a:

To estimate HIV incidence in household-based representative sample of men at baseline and post MC ASI. (Cohort A1 vs A2)

The sample size for the men’s Cohort A1 is 5,823 and for Cohort A2 is 6,165. Each person enrolled in Cohort A1 contributes 6 months of follow-up and in Cohort A2, each contributes 12 months of follow-up. The sample size is chosen to achieve sufficient “effective” person years to achieve 80% power to detect a 45% reduction in ratio of infection rates, assuming a Poisson distribution in each cohort of number of seroconversion events in total accumulated person years.

Note: Very similar sample sizes result from comparison of binomial probabilities of the proportion of the cohort infected in the pre vs. post MC ASI cohorts, provided exact methods are used. Poisson analysis is planned to accommodate varying lengths of follow-up time in the follow-up cohort.

- Men. The total number of person-years required to detect a 45% reduction in the HIV incidence rate from 2.0 per 100 person years (approximated baseline rate) to 1.1 per 100 person years (post-intervention) with a 1:2 ratio of person years in the two cohorts is 6,288. With a design effect of 1.25 and loss to follow-up of 10% and 15% in the pre- and post-MC ASI this yields a sample size of 5,823 men followed for 6 months and 6,165 men followed for 12 months in Cohort A1 and Cohort A2 respectively. (See Tables 1 and 2)

Table 1:

Effective person years required to detect 30-60% difference between infection rates with 6 month follow-up in Cohort A1, 12 month follow-up in Cohort A2, for two sided alpha of 0.05, and 80% power. Wald test statistic for slope in Poisson Regression, under assumption of simple random sample.				
λ_1	λ_2	Ratio λ_2/λ_1	Total Effective ¹ Person Years (Both serocohorts combined)	
0.0200	0.0140	0.70	15865	
0.0200	0.0130	0.65	11224	
0.0200	0.0120	0.60	8272	
0.0200	0.0110	0.55	6289	
0.0200	0.0100	0.50	4901	
0.0200	0.0090	0.45	3898	
0.0200	0.0080	0.40	3155	
0.0300	0.0210	0.70	10577	
0.0300	0.0195	0.65	7483	
0.0300	0.0180	0.60	5514	
0.0300	0.0165	0.55	4192	
0.0300	0.0150	0.50	3267	
0.0300	0.0135	0.45	2599	
0.0300	0.0120	0.40	2103	

¹Effective person years assume a simple random sample.

Number of households

The number of households required to achieve the effective sample size is shown in Table 2. The derivation of each of the adjustment factors is as follows:

- Design Effect: Design effect for HIV in men ages 15-49 of 1.25, and the DEFT of 1.32, are both based on the 2006-07 DHS.
- Household adjustment:
 - 13% will be vacant/non-contactable, 5% will refuse participation at the household level. Adjustment factor = $1/0.87 \times 0.95 = 1.21$
- Household individual adjustment
 - Men: 92% will have male residents within the eligible age range, 77% of men will be HIV uninfected, 99% will agree to cohort enrollment, 90% will be contactable, 95% will agree to pre-cohort survey. Adjustment factor = $1/(0.92 \times 0.77 \times 0.99 \times 0.90 \times 0.95) = 2.11$
- Loss to follow-up
 - Men: 90% and 85% of men will complete follow-up in the 6 and 12 month cohorts, respectively (accounting for loss-to-follow-up, interview/HIV test refusal at follow-up, data loss, and specimen loss totaling 10% and 15%, respectively). Lost to follow-up adjustment = 1.11 and 1.18

Table 2: Number of enrolled male participants, participating households and households in sample required to achieve the targeted effective number of person years.

Effective number person years	Design effect	Loss to follow-up adjustment	Number Males enrolled	Male household adjustment	Number of households participate	Household adjustment	Number of households sampled
Pre-MC ASI Male Seroincidence Cohort (Cohort A1) – 6 month follow-up period							
2096	1.25	1.11	5823	2.11	12301	1.21	14884
Post-MC ASI Male Seroincidence Cohort (Cohort A2) – 12 month follow-up period							
4192	1.25	1.18	6165	2.11	13023	1.21	15758

The decision to power the evaluation to detect a 45% reduction in incidence in men is based upon a combination of factors: 1) mathematical modeling estimations of HIV incidence reduction anticipated in men following MC scale-up to 80% coverage in 2011; and 2) meta-analyses of efficacy results from the 3 MC RCTs (See Figure 2). The proportional hazard risk ratio (efficacy) from the 2009 Cochrane Review meta-analysis using case analyses from the three MC RCTs was 0.46 (95% CI, 0.34 – 0.62), which equates to a 54% risk reduction against HIV acquisition [Sigfried, 2009].

Primary Objective #1b:

To estimate HIV incidence in household-based representative sample of women at baseline and post MC ASI (Cohort A1 vs A2)

Mathematical modeling estimation of HIV incidence reduction anticipated in women following MC scale-up to 80% coverage in 2011 is expected to produce less than a 45% reduction in women (See Figure 1). Newly diagnosing approximately 35,000 men and

enrolled approximately 4,500 on ART may also contribute to reductions in HIV incidence.

The household sample of 14,884 and 15,758 in pre- and post- MC-ASI is expected to yield an enrolled cohort of 7106 women and 7,524 in the pre- and post-MC ASI cohorts respectively. (See Table 3)

Number of effective women-years accumulated-

The number of effective women years accumulated from the household sample of 14,884 and 15,758 in pre- and post- MS-ASI is shown in Table 3. The derivation of each of the adjustment factors is as follows:

- Design Effect: Design effect for HIV in women ages 15-49 of 1.25, and the DEFT of 1.32, are both based on the 2006-07 DHS.
- Household adjustment
 - 13% will be vacant/non-contactable, 5% will refuse participation at the household level. Adjustment factor = $1/0.87 \times 0.95 = 1.21$
- Household individual adjustment
 - Women: 105% will have female residents within the eligible age range, 65% will be HIV uninfected, 99% will agree to cohort enrollment, 90% will be contactable, 95% will agree to pre-cohort survey. Adjustment factor = $1/(1.05 \times 0.65 \times 0.99 \times 0.90 \times 0.95) = 1.73$
- Loss to follow-up

Women: 92% and 88% of women will complete follow-up in the 6 and 12 month cohorts, respectively (accounting for loss-to-follow-up, interview/HIV test refusal, data loss, and specimen loss totaling 8% and 12%, respectively). Adjustment factor = $1/0.92 = 1.09$ and $1/0.88 = 1.14$ respectively.

Table 3: Number of enrolled female participants, given sample of 14,884 and 15,758 households in the pre- and post-MC ASI cohort.

Effective number person years	Design effect	Loss to follow-up adjustment	Number Females enrolled	Female household adjustment	Number of households participating	Household adjustment	Number of households sampled
Pre-MC ASIFemale Seroincidence Cohort (Cohort A1) – 6 month follow-up period							
2615	1.25	1.09	7106	1.73	12,301	1.21	14884
Post-MC ASIFemale Seroincidence Cohort (Cohort A2) – 12 month follow-up period							
5297	1.25	1.14	7524	1.73	13,023	1.21	15758

With total effective person years of 7912 in the women, assuming a seroincidence rate of 3.0 per 100 person years, and a sample ratio of 1:2, we have 68% power to detect a 30% reduction in HIV seroincidence and 82% power to detect a 35% reduction in HIV seroincidence.

Primary Objective #2a

To estimate HIV incidence rates in the highest risk age subsets of men ages 25-34 in the household-based, nationally representative sample for an additional 6-18 months after the MC ASI completion (Cohort B).

From the sample of 5823 men in the pre-MC-ASI cohort (Cohort Aa), we expect 25% of the men to be aged 25-34, a sample of 1456. From the sample of 6,165 men in the post-ASI cohort (Cohort A2), we expect 25% of the men to be aged 25-34, a sample of 1,541. If we compare the seroincidence in the 26-34 year old men 6 months prior to MC ASI to the seroincidence in the 18 months period (24-42 months following the end of the pre-MC-ASI cohort), we would have ~80% power to detect a 50% reduction in HIV seroincidence, assuming a pre-MC-ASI seroincidence of 5.0 per 100 person years, after accounting for lost to follow-up of 12% per year, and a design effect of 1.25 in each cohort

Primary Objective #2b

To estimate HIV incidence rates in the highest risk age subsets of women ages 18-24 in the household-based, nationally representative sample for an additional 6-18 months after the MC ASI completion (Cohort B).

From the sample of 7524 women in the post-ASI cohort (Cohort A2), we expect 29% of the women to be aged 18-24, a sample of approximately 2183. If we compare the seroincidence in the 6 months prior to MC ASI to the seroincidence at 24-42 months following MC ASI, we would have ~80% power to detect a 40% reduction assuming a seroincidence of 6.0 per 100 person years, after accounting for lost to follow-up of 10% per year, and a design effect of 1.25 in each cohort

Primary Objective #3

To estimate HIV incidence of circumcised compared to uncircumcised men in a household-based representative sample of men post- MC ASI (Cohort A2).

The 6165 men in the post-MC ASI cohort (A2) gives 71% power to detect a 55% decrease in the HIV incidence rate ratio between circumcised and uncircumcised men, assuming 80% of the men are circumcised and 20% are uncircumcised (i.e. a ratio of 4:1) and the seroincidence rate in the uncircumcised men is 2.5 per 100 person years, 12% loss to follow-up. If 2/3 of the men are circumcised, the power is increased to 83%. As the comparison will be within the cohort, no adjustment for design effect is assumed.

As the primary objectives capture the most important scientific objectives of importance, power consideration are only given for these objectives.

Secondary Objectives #8, and #9

- 8) To describe the concurrent CD4 count and viral load distributions in a nationally representative sample of HIV-infected men and women ages 18-49, in the context

of ART use.

